8.9. Other Considerations: Handling impact of COVID-19 pandemic

The present document and the analysis described in it, have been updated in compliance with the FDA **guidance** contained in the Conduct of Clinical Trials of Medical Products during the Covid-19 Public Health Emergency (Version March 2020, updated on August 30th 2021).

The Sponsor provided instructions to sites during the study in order to manage and mitigate the COVID-19 pandemic effects on the study, particularly allowing remote subject visits (refer to the Guidance and contingency plan from Sponsor to Sites (8)).

8.9.1. Handling Impact of COVID-19 in the Statistical Analysis All deviations related to the COVID-19 pandemic and resulting from the measures described in the Sponsor's contingency plan have been captured and discussed during the BDRM.

Sensitivity analyses have been planned based on the following considerations. Upfront it can be stated that:

- A tangible impact on measurements of body weight can be expected. Body weight values were reported by patient at each visit during a phone call. Patients were asked to use their own weight scale (analog or digital). This implies a lack of standardization and therefore to a certain degree of variability and lower accuracy.
- A minor impact is anticipated on eCOA endpoints. During remote visit on the phone, patient was asked to respond to each item of each questionnaire as per schedule at the given visit by delegated study personnel who entered responses in eCOA system accordingly, and data underwent to standard transmission process.
- There is no reason to expect any worsening in patient safety.

T AN001 Effective Date 25 JUL 2022 Approved Version 2.00

9. STUDY POPULATION

9.1. Trial Subjects

9.1.1. Analysis Sets

The following study populations (analysis sets) will be considered for analysis:

- The Intent-to-Treat (ITT) Set includes All randomized patients and will be analyzed as per planned treatment.
- The Full Analysis Set (FAS) includes all randomized patients who took at least one dose of trial medication and for whom any post-randomization data (in addition to the trial medication intake) are available. The FAS will be analyzed as per randomization.
- The Safety Set includes all patients who receive any study drug and will be analyzed as per actual treatment.
- The Per-Protocol (PP) set is subset of the randomized patients who do not have major protocol violations and will be analyzed as per actual treatment.

9.1.2. **Protocol Deviations**

Protocol deviations (PDs) were collected and documented by the study monitors and medical team throughout the study period. During the data cleaning process, PDs detectable programmatically in the clinical database were also identified and documented for final discussion and categorization during the BDRM.

Exact definition of major and minor protocol deviations affecting primary efficacy were specifically discussed and approved by Helsinn at the BDRM and documented in the meeting minutes.

The finalization of protocol deviations and exclusions from the Per Protocol set have been made prior to randomization code being revealed.

Minor and major protocol deviations identified will be summarized by treatment group and for all patients in the ITT Set

A listing of all protocol deviations will also be provided.

9.1.3. Disposition of Subjects and Discontinuations

All summaries will be presented on the ITT Set.

The number of subjects treated in the study will be presented, together with the number and percentage of subjects who completed the study and the number and percentage of subjects who withdrew from the study prematurely; a breakdown of the corresponding reasons for withdrawal will be presented. The number of subjects who discontinued the study treatment prematurely will also be presented with a breakdown of the corresponding reasons for study treatment discontinuation.

A tabulation of the number and percentage of subjects randomized at each site and country will be summarized for all patients in the ITT Set.

HHELSINN

30/66

9.2. Demographics and Other Baseline Characteristics

9.2.1. Demographics

Life Sciences

Subject demographics will be summarized using descriptive statistics for continuous variables and frequency distributions (number and percentage of subjects) for categorical variables. Summaries will be provided overall and by treatment group at Screening for all defined analysis sets.

The following demographic data and baseline characteristics will be summarized:

• Age at Screening

Business & Decision

- Gender
- Race and Ethnicity
- Height
- Weight at Screening
- BMI at Screening

If subjects have record of more than one race, then for the summary table, these subjects will be included in the Other Race group. BMI will be calculated from the height and weight values.

All demographic data and baseline characteristics will be listed for all patients in the ITT Set. In the demography listing, if a subject has more than one race recorded, then all races selected will be listed for that subject.

9.2.2. ECOG Status at screening

ECOG status at baseline (screening) will be summarized using frequency distributions (number and percentage of subjects). Summaries will be provided overall and by treatment group for all defined analysis sets.

ECOG status will also be listed for all patients in the ITT Set.

9.2.3. Stratification factors at V2 (randomization)

Chemotherapy line, Anti-cancer treatment (Immunotherapy/Non-immunotherapy) and 5-IASS score used as stratification factors at randomization will be summarized using frequency distributions (number and percentage of subjects) for categorical variables. Summaries will be provided overall and by treatment group for ITT set only.

All stratification factors will also be listed for all patients in the ITT Set.

9.2.4. Body Weight and 5-IASS at V1 (Screening) and V2 (Randomization)

Body Weight and 5-IASS score used as co-primary endpoint for the efficacy analysis, will be summarized using descriptive statistics for continuous variables. Summaries for screening and randomization visits will be provided in a single table overall and by treatment group for ITT set.

Body Weight and 5-IASS score at V1 and V2 will also be listed for all patients in the ITT Set.

9.2.5. Vital Signs at screening

Vital Signs collected at screening will be summarized using descriptive statistics for continuous variables. Summaries will be provided overall and by treatment group for all defined analysis sets.

The following Vital Signs data will be summarized:

- Systolic Blood Pressure
- Diastolic Blood Pressure
- Pulse Rate
- Respiratory Rate

Business & Decision

Life Sciences

Body Temperature

All data will be listed for all patients in the ITT Set.

9.2.6. Reproductive Status

Reproductive status information will be summarized using frequency distributions (number and percentage of subjects) for categorical variables. Summaries will be provided overall and by treatment group at Screening for ITT and Safety sets.

The following reproductive status information will be summarized:

- Patient childbearing potential
- Use of reliable contraceptive measures
- Reason of not being childbearing potential

All data will be listed for all patients in the ITT Set.

9.2.7. Prior Body Weight Loss at screening

Body Weight loss within 6 months prior to screening will be summarized using descriptive statistics for continuous variables. Summaries will be provided overall and by treatment group at Screening for all defined analysis sets.

All data will also be listed for all patients in the ITT Set.

9.2.8. Medical History and Concomitant Diseases

Medical history and concomitant diseases will be coded with MedDRA dictionary (version 22.0).

Medical history refers to all conditions that started and ended before the first dose of study drug.

Concomitant diseases refer to all conditions started before the first dose of study drug and with an end date on or after the first dose of study drug.

Medical history and concomitant diseases will be summarized in frequency tables by SOC and PT (sorted by descending frequency of SOC and then PT in the anamorelin arm) for ITT and Safety Sets.

A listing of Medical History and Concomitant diseases will also be provided for the ITT Set.

HELSINN

9.2.9. NSCLC status at Diagnosis and study Entry

NSCLC status at Diagnosis will be summarized using descriptive statistics for continuous variables and frequency distributions (number and percentage of subjects) for categorical variables. Summaries will be provided overall and by treatment group at Screening for ITT and Safety sets.

The following information will be summarized:

- Time to initial diagnosis at study screening (Year)
- Stage at Diagnosis (TNM classification)
- Overall stage
- Site of Metastasis

Business & Decision

Life Sciences

- Mutational Status and type of mutation
- TUMOR PD-L1 Expression

The same descriptive statistics will be provided for NSCLC status at Study Entry (excluding Time to initial diagnosis at study screening).

All NSCLC status data at diagnosis and study entry will be listed for the ITT Set.

9.2.10. Physical examination

Physical examination data will be summarized using frequency distributions (number and percentage of subjects). Each Body System examined (General Appearance, Head, Eyes, Ears, Nose and Throat, Skin, Neck and so on) will be provided overall and by treatment group at Screening for ITT and Safety sets.

All physical examinations will also be listed for all patients in the ITT Set.

9.3. Prior and Concomitant Medications/Procedures

Medication usage will be coded using the World Health Organization (WHO) Drug Dictionary (version WHO Drug Enhanced version Mar 2019 C3). Medications will be presented by WHO Drug Anatomical/Therapeutic/Chemical category and Active ingredient.

Summaries will be presented for prior and concomitant medications and procedures. All summaries will present the number and percentage of subjects for each medication/procedure.

Prior and concomitant medication/procedures will be described as first excluding NSCLC treatment/procedures, then only the cancer treatment (e.g.: chemotherapy) or procedures (e.g.: radiotherapy or surgery) will be presented.

The denominators for calculating the percentages will be based on the number of subjects in the ITT set.

Summaries will be provided overall and by treatment group for ITT and Safety sets.

All prior and concomitant medications/procedures presented in this section will be listed for patients in the ITT Set.

Life Sciences

9.3.1. Prior/Concomitant Medications (excluding NSCLC treatment)

Medications (excluding the NSCLC treatment) taken with an end date occurring before the first dose of study drug will be identified as prior medications.

Medications (excluding the NSCLC treatment) taken with a start date occurring on or after the first dose date or medications taken with a start date prior to the first dose date and an end date on or after the first dose date and a start date before EOT date will be identified as concomitant medications.

9.3.2. Prior/concomitant Procedures (excluding NSCLC treatment)

Procedures (excluding the NSCLC treatment) performed with an end date occurring before the first dose of study drug will be identified as prior procedures.

Procedures (excluding the NSCLC treatment) performed with a start date occurring on or after the first dose date or procedure performed with a start date prior to the first dose date and an end date on or after the first dose date and a start date before EOT date will be identified as concomitant procedures.

9.3.3. **Prior/Concomitant Cancer treatment**

Cancer treatment medications taken with an end date occurring before the first dose of study drug will be identified as prior cancer treatment.

Cancer treatment medications taken with a start date occurring on or after the first dose date or medications taken with a start date prior to the first dose date and an end date on or after the first dose date and a start date before EOT date will be identified as concomitant cancer treatment.

9.3.4. **Prior/concomitant Radiotherapy/Surgery**

Procedures (considering only those for cancer treatment, e.g. radiotherapy/surgery) performed with an end date occurring before the first dose of study drug will be identified as prior procedures.

Procedures (considering only those for cancer treatment, e.g. radiotherapy/surgery) performed with a start date occurring on or after the first dose date or procedure performed with a start date prior to the first dose date and an end date on or after the first dose date and a start date before EOT date will be identified as concomitant procedures.

9.4. Treatment Compliance

Compliance will be evaluated overall for the Safety Set, ITT Set and Per Protocol Set.

Treatment compliance will be calculated as:

Compliance (%) = (# tablets taken / # tables to be taken according to the study schedule).

Where:

Life Sciences

tables taken = total number of tables taken between the date of first intake (included) and the date of last intake (included), as collected in the drug accountability CRF form.

tables to be taken according to the study schedule = date of Visit 10 - date of Visit 2 +1.

Date of Visit 10 will be replaced by the date of premature treatment discontinuation for patients who discontinued treatment prematurely.

In case a patient completed the treatment but missed Visit 10 or in case a patient prematurely discontinued treatment and presented an EOT date, as recorded in the related CRF form, which is considered as implausible (i.e.: EOT date greater than 25 days after the date of the first dose of the last kit), then the corresponding Visit 10 date or EOT date will be replaced with the date of last visit performed + 24 days.

If a subject returns all study medication that was dispensed, then the subject will not be classified as treated.

In case of missing drug accountability data, it will be assumed that no tablets were taken for the corresponding days with missing data.

For patients with kit(s) not returned, the information available in the drug administration CRF form about the documented tablet intake during the applicable study visit (i.e.: the study visit during which the first tablet from the kit – then never returned – was administered) will be used to add such one single day of documented treatment. For patients with kit(s) not returned and not having any information in the drug administration CRF form, i.e., there is no evidence that at least one tablet was taken, the number of tables taken will be assumed as 0.

A patient will be considered compliant with the therapy if his/her overall compliance is higher or equal to 80%.

Compliance will be reported numerically using descriptive statistics and categorically (using categories <80%, $\ge80\%$ to $\le100\%$, and >100%), by treatment group.

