5.8 Administration of Study Treatment

At Day 1 (Visit 2), after confirming patient's eligibility, the Investigator or designee will get connected to the IWRS to randomize the patient. An IWRS will be employed for the randomization activities taking into account the stratification factors (See Section 9.1). The IWRS will assign a study kit number to the patient and the Investigator (or Investigator's designee) will receive the IWRS notification mentioning the study kit number assigned to the patient for which the request was made. The hospital pharmacist, or designated responsible person, will select from the study kits stored at the site pharmacy the corresponding kit as indicated by the IWRS and fill-in the blank space(s) on the outer study kit label with the patient's identification number which was assigned by IWRS during screening.

Allocation and distribution of the study kit to the Investigator or Investigator's designee is tracked by attaching the study kit label peel-off portion onto the study site drug accountability log (or similar document).

Adequate written instructions (in form of a Study Drug Manual) for use for the pharmacist or designated person will be provided to him/her for the management of the study kit at each study site.

The relevant labels on the study kits will be filled in according to the provided instructions.

Patients will take 1 tablet on Day 1 (if a fasting state is not possible on Day 1, the patient will start study drug on Day 2) and daily thereafter. Patients will be supplied with study drug at Visit 2 and resupplied at Visit 3 (Week 3), Visit 4 (Week 6), Visit 5 (Week 9), Visit 6 (Week 12), Visit 7 (Week 15), Visit 8 (Week 18) and Visit 9 (Week 21).

Tablets of study drug will be taken orally in mornings while fasting at least 1 hour before breakfast. Water is permitted prior to and with study drug.

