6 STUDY CONDUCT

6.1 Study Procedures by Time Point

6.1.1 Visit 1 (Screening, Day -7 to Day -1)

If the Investigator considers a patient to be potentially eligible for the study, written informed consent for participation in the study must be obtained before any study-related procedures starts. The patient will be screened within 7 days prior to randomization (Day 1) and study drug administration; the following procedures will be performed, and data collected during this visit for eligibility purposes:

- Informed consent.
- Significant medical history.
- A dedicated physical examination with focus to monitoring signs and symptoms of edema (see Section 7.2.2.1 for details); Results of this PE will be inserted in source data and in the relevant pages of eCRF.
- ECOG Performance Status.
- Vital signs (including pulse rate, systolic and diastolic blood pressure after at least 5 minutes rest in semi-supine position, respiratory rate and body temperature).
- Body weight, height and BMI.
- Prior body weight loss will be verified by the use of patient medical charts; this information can be retrieved either by hospital or family doctor medical charts.
- 12-Lead ECG, in triplicate.
- Chemistry and hematology testing, including HbA1c under fasting conditions.
- Urine pregnancy test for females of childbearing potential.
- Urinalysis under fasting status.
- Administration of FAACT 12-item A/CS domain and PGIS questionnaires for body weight and anorexia.
- CT scan for tumor assessment. The baseline tumor assessment may have been obtained within 28 days of the first dose of study drug (see Section 7.2.7).
- AEs will be collected from the Informed consent signature up to Follow-up visit.
- Prior and concomitant medications data will be collected.

Based on the relevant above mentioned assessments outcome, the Investigator will decide if the patient is eligible for the study. If eligible, patient will be reminded to come back to clinical site under fasting condition for Visit 2 for laboratory assessments and to be administered with study drug.

6.1.2 Visit 2 (Randomization/Treatment Period, Day 1): Week 1

Patient will arrive at the clinical site under fasting condition. Once at the site, Investigator or designated personnel will re-check the following criteria:

- inclusion criterion # 10 (Urine pregnancy test) and
- exclusion criteria # 3, 5, 6, 7g, 9.

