- CT scan may be performed as per standard local practice. Exact time point for CT scan will depend on the investigator's standard plan at each site (see Section 7.2.7).
- Adverse Events, procedures, and hospitalizations assessment.
- Administration and completion of
 - FACIT questionnaires (includes all 4 domains PWB, FWB, SWB, and EWB domains of FACT-G, 12-item A/CS domain and FACIT-F fatigue domain),
 - Hunger Assessment questionnaire.

Questionnaires will be administered in the order presented here and administered from 1 to 4 hours post study drug administration.

• Check and record Concomitant medications (not including NSCLC treatment regimen).

- NSCLC treatment regimen and any dose adjustments, as and if applicable.
- New study kit will be dispensed, and patient will return wallet card from previous visit; compliance will be checked.
- The patient will also be reminded about the prohibited concomitant medications (see Section 5.13.2 for details).
- Patient will also be reminded to come back to clinical site in 3 weeks for next visit and be reminded to arrive at the hospital under fasting conditions.

6.1.10 Visit 10 (Day 169+3): Week 24

The patient will return to the trial site on Visit 10, at Day 169 (+3), approximately 3 weeks after Visit 9. Patient will arrive at the hospital under fasting conditions.

The patient will undergo the following procedures/assessments:

- Patient will return wallet card from previous visit; compliance will be checked.
- Study drug administration (last dose).
- Laboratory assessments, including:
 - Chemistry,
 - Hematology,
 - HbA1c Assessment.
- Urine pregnancy test for females of childbearing potential.
- Urinalysis under fasting status.
- Vital signs including pulse rate, systolic and diastolic blood pressure after at least 5 minutes rest in semi-supine position, respiratory rate and body temperature).
- Body weight via scale measurement, to be done prior to study drug administration.
- A dedicated physical examination with focus to monitoring signs and symptoms of edema (see Section 7.2.2.1 for details); Results of this PE will be inserted in source data and in the relevant pages of eCRF.
- 12-Lead ECG (1 hour post dose), in triplicate.
- CT scan may be performed as per standard local practice. Exact time point for CT scan will depend on the investigator's standard plan at each site (see Section 7.2.7).
- Adverse Events, procedures, and hospitalizations assessment.
- Administration and completion of

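### SAP 9.4 counts tablets due from Visit 2 even for patients permitted to start on Day 2, which understates their compliance by one tablet and moves a few across the 80% line

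*SAP*

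**What the plan says.** SAP 9.4 defines compliance as tablets taken divided by tablets due.

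- **Taken:** "total number of tables taken between the date of first intake (included) and the date of last intake (included"), from the drug accountability form.
- **Due:** "tables to be taken according to the study schedule = date of Visit 10 - date of Visit 2 +1".
- **End-date adjustment:** "Date of Visit 10 will be replaced by the date of premature treatment discontinuation for patients who discontinued treatment prematurely". Further rules replace the end date when Visit 10 was missed or the end-of-treatment date is implausible. No rule changes the start date.
- **Cut:** "A patient will be considered compliant with the therapy if his/her overall compliance is higher or equal to 80" percent. Results are tabulated by arm as below 80%, 80 to 100%, and above 100%, for the Safety, ITT and PP sets.

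Visit 2 is Day 1 (Protocol 6.1.2). Protocol 5.8, in agreement with the synopsis, provides that "if a fasting state is not possible on Day 1, the patient will start study drug on Day 2".

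**The concern.** The numerator starts at first intake and the denominator at Visit 2. For a Day 1 starter these are the same day. For a patient using the fasting exception they are one day apart, and the denominator contains a tablet that the protocol did not ask for. That patient cannot reach 100% however well the schedule is followed.

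The loss is one tablet, or 100/d percentage points for a patient otherwise at full adherence who stops on Day d. Because the denominator ends at discontinuation, the loss grows as treatment gets shorter, and SAP 8.2.2 and 12.1.1.2 do anticipate treatment stops. At stake are the compliance percentages and the share of patients reported below 80%. The error can only lower a Day 2 starter's score.

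**Working it through.** **Inputs.** Visit 2 = Day 1 (Protocol 6.1.2). Visit 10 = Day 169, with a window of +3 days, and the last dose is taken there (Protocol 6.1.10). One tablet daily, first tablet on Day 2 under the fasting exception (synopsis, Protocol 5.8). Cut: 80% or more is compliant (SAP 9.4). The documents contain no worked compliance figure to reproduce.

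**Check of the formula.** Day 1 starter, completes on Day 169, misses nothing: due = 169 - 1 + 1 = 169, taken = 169, compliance 100%. The rule is right when the first tablet is taken at Visit 2.

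**Day 2 starter who misses nothing.** Assume the last tablet and the recorded discontinuation both fall on Day d.

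- taken = d - 2 + 1 = d - 1
- due = d - 1 + 1 = d
- compliance = (d - 1)/d, below 0.80 only if d < 5

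| Stop day d | SAP 9.4 score | Category | Due counted from Day 2 |
|---|---|---|---|
| 2 | 1/2 = 50.0% | below 80% | 1/1 = 100% |
| 3 | 2/3 = 66.7% | below 80% | 2/2 = 100% |
| 4 | 3/4 = 75.0% | below 80% | 3/3 = 100% |
| 5 | 4/5 = 80.0% | compliant | 4/4 = 100% |
| 8 | 7/8 = 87.5% | compliant | 7/7 = 100% |
| 22 | 21/22 = 95.5% | compliant | 21/21 = 100% |
| 85 | 84/85 = 98.8% | compliant | 84/84 = 100% |
| 169 | 168/169 = 99.4% | compliant | 168/168 = 100% |

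**Day 2 starter who missed tablets.** With k tablets taken, the category changes when k/(d - 1) is at least 0.80 but k/d is below it, that is, when 0.8(d - 1) ≤ k < 0.8d. This interval has width 0.8, so it holds at most one whole number. It holds none when d is a multiple of 5 and exactly one otherwise.

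| Stop day d | Interval for k | k | SAP 9.4 | Due counted from Day 2 |
|---|---|---|---|---|
| 8 | 5.6 to 6.4 | 6 | 6/8 = 75.0% | 6/7 = 85.7% |
| 22 | 16.8 to 17.6 | 17 | 17/22 = 77.3% | 17/21 = 81.0% |
| 169 | 134.4 to 135.2 | 135 | 135/169 = 79.9% | 135/168 = 80.4% |

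**Sensitivity to the end date.** The documents do not say how the recorded discontinuation date relates to the last tablet. If it is one day later, a Day 2 starter who misses nothing scores (d - 2)/d. This is below 80% for recorded dates up to Day 9 (7/9 = 77.8%) and reaches 80.0% on Day 10 (8/10). Part of that loss is not due to the start date: a Day 1 starter with discontinuation recorded on Day 4 also scores 3/4 = 75.0%. Correcting the start alone gives (d - 2)/(d - 1), for example 3/4 = 75.0% on Day 5 and 4/5 = 80.0% on Day 6.

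**The case against.** The strongest case against the point is that it is tiny. A Day 2 start is an exception: Protocol 6.1.2 expects the patient to arrive fasting, take the drug on site and have an ECG one hour later. SAP 9.4 also accepts coarser approximations. Missing accountability data count as no tablets taken, an unreturned kit earns at most one day, and an implausible end date becomes the last visit plus 24 days. All of this stands and limits the weight of the point. It does not make the rule right, because those approximations deal with missing or implausible data, whereas here the dates are known and the rule still counts a tablet that was not due.

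A second objection is that the obvious remedy, counting from first intake for everyone, does harm. This also stands. Compliance is reported on the ITT set, where a never-treated patient has no first intake. And a patient who first dosed on Day 6 without any allowance would score 100%.

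A third concerns the premise. Protocol 5.3 gives a Day 1 start and does not repeat the exception found in the synopsis and 5.8. Those passages must be reconciled; the calculation here applies the exception as the synopsis and 5.8 state it.

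Three stronger readings are tempting but not supported:

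- *That early stoppers who miss nothing generally fall below 80%.* From Day 5 on they do not, if discontinuation is recorded on the day of the last tablet.
- *That the PP set or an efficacy result is distorted.* SAP 9.1.1 and 9.1.2 base the PP set on major deviations settled at the blinded review, and the documents do not say that compliance under 80% is one of them.
- *That SAP 9.4 is wrong because exposure in SAP 11.1 starts at first intake.* Time on drug and tablets taken against schedule are different quantities and may start on different days. The fault lies between SAP 9.4 and the permitted Day 2 start.

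**Conclusion.** The point holds as a minor error of definition. Every permitted Day 2 starter is charged one tablet too many. A completer who misses nothing loses 0.6 percentage points. A patient who misses nothing is put below 80% only when treatment stops on Day 2, 3 or 4. Among patients who missed tablets, at most one tablet count per stop day is put in the wrong category.

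This rests on one tablet per day, discontinuation recorded on the day of the last tablet, and the fasting exception as written in the synopsis and Protocol 5.8. The number of Day 2 starters is not given, so the number of patients affected cannot be stated. What is shown to be affected is the descriptive compliance summary; no consequence follows for the co-primary or other efficacy analyses.

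**What to change.** In SAP 9.4, make the start of the denominator depend on the first intake:

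- **First intake on Day 1:** keep the date of Visit 2.
- **First intake on Day 2 under the fasting exception:** use the date of first tablet intake, which is Visit 2 plus one day.
- **First intake after Day 2:** count from Day 2 if the fasting exception is documented, otherwise from Visit 2, so that longer delays are not credited.
- **Never treated (ITT set):** keep Visit 2 and report 0%.

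The date and time of the Visit 2 dose are already to be recorded (Protocol 6.1.2), and the schedule notes call for fasting status in the CRF. The cost is a sentence or two in the SAP and a small program change. The change does not remove a shortfall that arises because discontinuation is dated after the last tablet; that would need its own end-date convention.
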